5.20 Detail of contact points with participants

Eligibility (contact 1 – phone call)

Potentially eligible participants will receive a phone call (call 1) from a study RA who will administer a screening questionnaire in Drupal software to confirm eligibility. The screening questionnaire will incorporate relevant inclusion/exclusion criteria.

Support to download study smartphone app, complete consent and baseline questionnaire, and watch study tutorials (contact 1)

Following screening, the RA will ensure participants have received and read the Participant Information Sheet (emailed following referral). The RA will then send a link to download the study smartphone app and an access code with instructions to complete the consent form and baseline questionnaire via text message. The RA may stay on the telephone to guide participants to download the study smartphone app and to complete the consent form and baseline questionnaire (in app). Participants are directed to watch study tutorials on how to collect shopping purchases, urine, and BP data and advised that study staff are available to answer any questions if needed during the study period. However, the participant may choose to hang up and complete these tasks in their own time or may book an appointment to come into the University of Grafton Campus Clinic to complete these tasks face-to-face. If the participant chooses to complete consent in their own time and consent has not been completed within five days, one notification and follow-up phone call will be made to the participant. Following call 1 and completion of the consent form and baseline questionnaire, a study RA will courier the participant a study pack including the BP monitor, urine collection equipment and a study flow

Not for Public Circulation or Reproduction

chart. If the baseline questionnaire has not been completed within one-week follow-up phone call(s) (call 1b & c) may be required.

Follow up on receipt of study pack (contact 2 – phone call or text message)

Following courier of the study pack, the RA will phone or text message the participant (contact 2) a few days later to check they have received it and to offer support on collection of BP measures, returning a spot urine sample, and scanning barcodes of shopping purchases. Participants will also be reminded of the study phone number to call or text, and email address to ask any further questions, as well as the study video tutorials explaining procedures.

Notification of randomisation (contact 3 – text message)

At the end of baseline (end of week -1), a study RA will confirm eligibility (minimum of six BP measures received, one urine sample, and 10 scanned food purchases) and text the participant (contact 3) to notify them of the group they have been allocated to. The RA will activate the participants study smartphone app to receive the appropriate notifications, based on their allocation. The RA will call participants in the intervention group to support them download the SaltSwitch smartphone app, enter a code to 'unlock' it, and watch a short tutorial (within the app) on how to use it. The intervention group will be notified that they will receive a supply of study salt in the mail.

Study end (contact 4 – a. Phone call and b. Email/Letter)

Participants will receive a notification via the study app at the end of week 12 to complete the follow-up questionnaire. If the follow up questionnaire has not been completed within one week following the end of the study, a follow-up phone call(s) (contact 4a.) may be required. On completion of the follow up questionnaire participants will receive a notification thanking them for their participation, a summary of their BP measures over the study, and more information about the dietary salt substitute. A study completion email or letter (contact 4b.) will also be sent to participants which will include instructions (1) to download the BlipCare smartphone app to monitor their BP measures post study-completion (2) to change the settings in their phone to enable them to continue using the SaltSwitch app but to cease collection of their use of the app by Google Analytics if in the intervention group (3) to download the SaltSwitch app (control group) and on how to purchase the dietary salt substitute. The RA will disconnect the participant's blood pressure monitor from the study system to stop data being sent to the study team.

Not for Public Circulation or Reproduction

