5.14 Follow-up assessment

Follow up assessment will comprise four components: (1) the follow up questionnaire, (2) return of a spot (casual) urine sample during week 12 (+/- one week)., (3) collection of home-based BP

Not for Public Circulation or Reproduction

measures during week 12 (+/- one week), and (4) collection of barcodes for all packaged foods and beverages bought into the home for consumption during weeks 11 and 12 (+/- one week)..

Follow up questionnaire

At the end of the 12-week intervention period, participants will be prompted by the study app to complete the follow up questionnaire. Two text reminders will be sent five days apart. If the follow up questionnaire has not been completed within four weeks of the end of the intervention period, then follow up data will be considered missing.

The follow up questionnaire will collect the following information:

- 1. Change in habits regarding salt added to food and/or take away consumption
- 2. Change in the in the number of participants household food is usually purchased for
- 3. Change in body weight (self-reported)
- 4. Use and acceptability of the SaltSwtich smartphone app (intervention group only)
- 5. Use and acceptability of the dietary salt substitute and left-over study salt (intervention group only weighed if possible or estimated if not possible)
- 6. Left-over regular table salt (control group only weighed if possible or estimated if not possible)
- 7. Details of any cardiac event in the past 12 weeks (prompt to complete Serious Adverse Event form if appropriate)
- 8. Number of visits to the Dr and/or hospital during the study period, and number of these visits which are primarily due to their BP or medication for their BP
- 9. Use of meal boxes during the study period e.g. My Food Bag, WOOP.

Collection of BP, urine and packaged food purchases

A spot urine sample (week 12 +/- one week) home-based BP measures (week 12+/- one week), and barcodes for packaged food and beverage purchases (weeks 11 and 12 +/- one week). will be collected as per the baseline phase. Participants will be couriered enough equipment at baseline for collection and return of the second spot urine sample.

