5.19 Schedule of intervention and follow-up

Participants will be notified by a study RA (via telephone) as to their treatment allocation.

Intervention participants will be sent a text with a link to download the SaltSwitch smartphone app in the iOS or Android app stores, and a code to unlock the app. They will also be sent a supply of study salt (dietary salt substitute) via courier and a link to the intervention tutorial/video (via a notification from the study smartphone app), the latter which will explain how to use the two components of the BP lowering intervention. Intervention participants will receive weekly notifications reminding them to use the SaltSwtich app when shopping for household food, and to use the study salt in place of regular table salt (but not to increase their intake/use of salt).

Control participants will receive one notification at the beginning of the intervention phase (via email) containing a link to information on heart-healthy eating on the Heart Foundation of NZ website, and will be advised not to change their regular salt intake.

At the end of the intervention period participants in the intervention group will receive instructions to ensure they are able to continue using the SaltSwitch smartphone app, but their study data will cease to be collected/recorded in Google Analytics. Control group participants will receive a information on how to download the SaltSwitch app. Both groups will be given information about how to purchase the dietary salt substitute (or a similar product available for sale in New Zealand). Participants will be allowed to keep their BP monitor and will be provided with information on how to download the BP monitor smartphone app to receive a summary of their BP measures collected during the study (and any additional BP measures they collect after study end).

Participants in the intervention group who complete and return their final urine sample will also be eligible to enter a draw to win one of five \$100 grocery vouchers. To enter the draw, participants must indicate your interest on the consent form and complete and return their final urine sample. Winners will be contacted by phone and email at the end of the study (estimated date March 2021). If no response is received within 14 days of notification, another winner will be drawn at random.

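### Study-end information on the salt substitute and SaltSwitch can reach controls up to one week before the primary-outcome urine sample is due, because its release is not tied to receipt of the final data

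*Protocol*

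**What the plan says.** **Follow-up windows.** Protocol section 5.14 specifies "return of a spot (casual) urine sample during week 12 (+/- one week"). The same one-week tolerance applies to the week-12 home BP readings and to barcode scanning in weeks 11 and 12.

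**Questionnaire and its consequence.** Section 5.20 states: "Participants will receive a notification via the study app at the end of week 12 to complete the follow-up questionnaire". It continues: "On completion of the follow up questionnaire participants will receive a notification thanking them for their participation", together with "a summary of their BP measures over the study, and more information about the dietary salt substitute". This message is not limited to one arm.

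**Completion letter.** Section 5.20 adds: "A study completion email or letter (contact 4b.) will also be sent to participants". Among its instructions are how "to download the SaltSwitch app (control group) and on how to purchase the dietary salt substitute". No trigger is given for it there. Section 11.3 places the final email or letter at completion of the study, without defining that point against the data windows.

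**Release to controls.** Section 5.19 describes what happens when the intervention period ends, and within that paragraph says: "Control group participants will receive a information on how to download the SaltSwitch app". Both arms are also told how to buy the substitute or a similar product.

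**Monitor.** The last sentence on study end in section 5.20 is: "The RA will disconnect the participant's blood pressure monitor from the study system to stop data being sent to the study team". It carries no time or condition. Section 11.3 mentions notice of the disconnection alongside the final letter.

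**The concern.** The protocol takes care to keep the intervention away from controls during the trial. The unlock code for SaltSwitch is partly meant to make control access less likely (section 5.4), and controls are advised to leave their usual salt intake unchanged (section 5.19). The study-end steps can undo both measures while outcomes are still being collected.

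The primary outcome rests on a single spot urine sample at follow-up. If a control gives it after acting on the released information, there is no other follow-up sample to set against it. Packaged-food sodium, a secondary outcome, is what SaltSwitch is designed to change, and scanning may also run into the extra week. Any response by controls would tend to narrow the difference between the arms.

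The start of the trial is handled differently. Before allocation is notified, the research assistant confirms that BP readings, a urine sample and scanned purchases are in (section 5.20, contact 3). No such check is stated before the study-end steps.

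**Working it through.** This is a question of timing, so the main check sets the sections side by side.

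| Step | Earliest time as written | Condition on final data | Source |
|---|---|---|---|
| Questionnaire prompt | End of week 12; twelve weeks after randomisation | None | 5.20; 11.3 |
| Salt-substitute information, both arms | On questionnaire completion | None | 5.20 |
| SaltSwitch information to controls, purchase advice to both arms | End of intervention period (end of week 12) | None | 5.19 |
| Completion letter | No trigger in 5.20; completion of the study in 11.3 | None | 5.20; 11.3 |
| Monitor disconnection | Not stated | None | 5.20; 11.3 |
| Urine, BP and barcode windows close | End of week 13 | n/a | 5.14 |

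**Overlap.** End of week 13 minus end of week 12 = up to one week.

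**Check on the week count.** Appendix 2 dates the follow-up questionnaire to week 14. With two baseline weeks and twelve intervention weeks, 2 + 12 = 14, so this is the end of intervention week 12. It does not move the prompt beyond the urine window.

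**Who is affected.** Only controls who (a) have been sent the information, (b) have not yet given urine and (c) act on it before doing so. The protocol gives none of these shares.

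**The design figure.** Inputs from section 6.1: 0.33 SD, SD 1400 mg/day, 80% power, two-sided 5%, 10% loss.
- Target difference: 0.33 × 1400 = 462 mg/day.
- Required n per arm (t-test): 146. Allowing for loss: 146 / 0.9 = 162.2, rounded up to 163, or 326 in total. This matches the protocol.
- Power with 163 × 0.9 = 146.7 evaluable per arm (normal approximation): 0.807.

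**Sensitivity of that figure (assumptions, not estimates).** Let f be the share of controls sampled after release, and g the average fraction of the 462 mg/day that they achieve by then. The difference becomes 462 × (1 − f × g).

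| f | g | Difference (mg/day) | Power |
|---|---|---|---|
| 0 | n/a | 462 | 0.807 |
| 5% | 25% | 456 | 0.797 |
| 10% | 25% | 450 | 0.787 |
| 10% | 50% | 439 | 0.766 |
| 20% | 50% | 416 | 0.720 |

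The table shows only how the design would respond. The 462 mg/day is the design difference for twelve weeks of the app plus supplied salt. A control would have at most a week, so large values of g are hard to defend.

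**The case against.** The strongest case on the other side is that the exposure is narrow and weak.

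- The target is week 12 itself, and the extra week is a tolerance. Many participants will have finished sampling before any message goes out.
- The questionnaire is accepted for up to four weeks after the intervention ends (section 5.14). Late responders will often trigger the message after the urine window has closed.
- Controls receive information, not the intervention. No salt is sent to them, and the trial product is not sold in New Zealand, although similar products are sold in some supermarkets (section 5.4). A control would have to read the message, obtain a product or shop with the app, eat accordingly and then give urine, all within about seven days.

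This stands as an argument about size. It does not remove the gap. The release in section 5.19 depends on the end of the intervention period rather than on the questionnaire, and neither route waits for the sample.

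Some stronger readings are tempting but lack support:

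- **Monitors are disconnected once the questionnaire is done.** A reader might infer this from the order of sentences in section 5.20, but no trigger is stated. Section 11.3, which mentions the disconnection with the final letter, is compatible with its following data collection. Week 12 has in any case ended when the questionnaire is prompted, so only readings in the extra week could be at risk.
- **Questionnaire completion releases SaltSwitch to controls.** In section 5.20 the download instruction belongs to the separate completion letter. Its timing comes from section 5.19 or 11.3, and these differ.
- **The BP summary contaminates the primary outcome.** Participants already take their own readings at home, and the summary conveys neither intervention component.

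**Conclusion.** The point holds as a timing gap. As written, controls can be informed about both intervention components up to one week before giving the primary-outcome sample, with BP and barcode collection also still open. Sections 5.19, 5.20 and 11.3 also disagree, or are silent, on when the completion steps occur.

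The likely direction is dilution of the sodium difference. The size cannot be derived from the protocol, which gives neither the share of late samples nor any figure for how quickly controls would respond. It is probably small, given the short exposure and the reliance on products that controls obtain themselves. Loss of BP readings in the extra week is possible, because disconnection is untimed, but the protocol does not prescribe it. The case for acting is that the exposure is created by the protocol itself and costs very little to remove.

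**What to change.** Reconcile sections 5.14, 5.19, 5.20 and 11.3 with one common rule. The salt-substitute information, SaltSwitch access for controls, the completion letter and monitor disconnection should occur only after the final urine sample, BP readings and barcodes have been received, or when the one-week tolerance has closed, whichever is first. Completion of the questionnaire should not trigger any of them. State in section 11.3 that completion of the study means this same point.

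The cost is a changed app or research-assistant trigger, with no added visit, sample or measurement. The downside is that some participants receive the information up to about a week later than they otherwise would.

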5.21 Table 1: Summary of SALTS trial stages and procedures

Assessment	Referral	Screening	Baseline	Randomisation	Mid study	Follow-up
Timing	Recruitment	Pre-baseline	Week -2/-1	Week 1	Week 6	Week 12
Method of contact and data collection	Face-to-face (malls, pharmacies, GP clinics)	Contact 1	Contact 1, API, courier, study smartphone app	Contact 3, courier	API	Contact1, API, courier, study smartphone app
Referral						
Name, initials, phone number, email	√					
Eligibility 1 (smartphone ownership, BP)	√					
Physical measures (height, weight, BP)	√					
Referral number allocated	√					
Participant Information Sheet emailed	√					
Screening						
Verbal consent to screening		√				
Gender		√				
Eligibility 2 (type of smartphone, date of birth, English, contribute to household shopping, current FoodSwitch use, recent CVD event, heart failure, contraindications, holidays)		V				
Screening number linked to referral number		√				
Informed consent						
PIS read and understood, consent in app		\checkmark				
Registration number allocated and linked to screening number		V				
Study smartphone app downloaded						

Confidential

Not for Public Circulation or Reproduction

Assessment	Referral	Screening	Baseline	Randomisation	Mid study	Follow-up
Timing	Recruitment	Pre-baseline	Week -2/-1	Week 1	Week 6	Week 12
Method of contact and data collection	Face-to-face (malls, pharmacies, GP clinics)	Contact 1	Contact 1, API, courier, study smartphone app	Contact 3, courier	API	Contact1, API, courier, study smartphone app
Tutorials completed for collection and return of BP, urine, shopping purchase data		$\sqrt{}$				
Baseline questionnaire						
Initials, date of birth			\checkmark			
Discretionary salt			\checkmark			
Preference for salty food			√			
Use of nutrition labels			\checkmark			
No. household members groceries bought for			√			
Existing health conditions			√			
Concurrent medications			√			
Ethnicity			√			
Employment			√			
Household income			√			
GP contact information			√			
Study pack 1 sent to participant						
BP monitor, urine collection equipment, study flow chart			√			
Baseline measures						

Confidential

Not for Public Circulation or Reproduction

Assessment	Referral	Screening	Baseline	Randomisation	Mid study	Follow-up
Timing	Recruitment	Pre-baseline	Week -2/-1	Week 1	Week 6	Week 12
Method of contact and data collection	Face-to-face (malls, pharmacies, GP clinics)	Contact 1	Contact 1, API, courier, study smartphone app	Contact 3, courier	API	Contact1, API, courier, study smartphone app
Twice daily home-based BP measures during week -1			√			
1x urine sample couriered to researchers						
Barcodes scanned using study app			√			
Randomisation						
Randomisation recorded				√		
Study pack 2 sent to participant						
Dietary salt/salt substitute				√		
Mid study measures						
Twice daily home-based BP measures during week 6					V	
Follow up measures						
Twice daily home-based BP measures during week 12						V
1x sample couriered to researchers						√
Barcodes scanned using study app						√
Follow up questionnaire						
Salt added to food (change)						√
No. household members groceries bought for						V

Confidential

Not for Public Circulation or Reproduction

Assessment	Referral	Screening	Baseline	Randomisation	Mid study	Follow-up
Timing	Recruitment	Pre-baseline	Week -2/-1	Week 1	Week 6	Week 12
Method of contact and data collection	Face-to-face (malls, pharmacies, GP clinics)	Contact 1	Contact 1, API, courier, study smartphone app	Contact 3, courier	API	Contact1, API, courier, study smartphone app
Weight						V
Use and acceptability SaltSwitch app (intervention group only)						V
Use and acceptability of study salt, and remaining salt substitute/salt						V
Details of adverse events						V
Visits to the Dr and/or hospital, and visits due primarily to BP or medication for BP						V
Use of meal boxes e.g. My Food Bag						V

Not for Public Circulation or Reproduction

6. Statistical Considerations

6.1 Sample size

A total of 326 participants (163 per group) will provide 80% power at a 5% level of significance (two-sided) to detect a minimum effect size of 0.33 standard deviation (SD) in the primary outcome measure between groups at week 12 allowing for 10% loss to follow-up. This effect size is based on the SD derived from the SaltSwitch pilot study data (1400mg/day) where estimations of 24hr urinary sodium excretion were calculated using spot urine samples and a standard urine volume of 1.99L.

6.2 Statistical analysis

Statistical analysis will be performed on an intention-to-treat (ITT) basis, using SAS version 9.4 (SAS Institute Inc. Cary NC, USA). All statistical tests will be two-sided at 5% significance level. Trial results will be reported according to CONSORT 2010 guidelines for parallel group randomised trials.

6.2.1 Baseline characteristics

Baseline characteristics of all randomised participants will be summarised using descriptive statistics. Continuous variables will be described as numbers of observed and missing values, mean ± standard deviation. Categorical variables will be described as numbers and percentages. Results will be presented for each of the two treatment arms overall, and by ethnicity (Māori vs non-Māori) and age group (<55yrs and 55yrs+) separately as stratification factors. Since any differences between randomised groups at baseline could only have occurred by chance, no formal significance testing will be conducted.

6.2.2 Treatment effects

The primary outcome will be analysed using linear regression model adjusting for baseline outcome value and stratification factors. Model-adjusted mean differences between two groups will be estimated with 95% confidence interval and p-value. Multiple imputation will be used on missing primary outcome data in the primary intention to treat (ITT) analysis; this method creates multiple imputed datasets for incomplete outcome variables that are analysed using same regression models and combined for one inference. The Markov chain Monte Carlo method will be used to produce the parameter estimates, assuming the data are from a multivariate normal distribution and are missing at random. Sensitivity analyses using different assumptions on the missing data, e.g. complete case analysis and last value carried forward, will also be considered to test the robustness of main trial analysis. Per protocol analysis will be performed for participants with no major protocol violations. Generalised linear regression models will be used to analyse secondary outcomes, using a link function appropriate to the distribution of outcome variable. Similar to the primary outcome analysis, the regression model will adjust for baseline outcome value and stratification factors where appropriate. Model-adjusted group differences will be presented with 95% confidence intervals and p-values. For the primary and key secondary outcomes, the heterogeneity of treatment effects between Māori and non-Māori participants will be tested using an interaction term between treatment group and ethnicity in the main model, and also for participants in two different age groups (<55yrs and 55yrs+).

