5.10 Participant screening

Potentially eligible participants will receive a follow up phone call from a study RA and a screening questionnaire will be administered. The screening questionnaire will collect date of birth and gender (male, female, gender diverse, prefer not to specify), and information on remaining inclusion/exclusion criteria relevant to the screening period: type of smartphone, contribution to household grocery shopping (or willing to for the study period), able to read and understand English, current use of a dietary salt substitute or the FoodSwitch app, contraindication to reducing salt or increasing potassium in their diet, recent stroke or cardiovascular event, or diagnosed heart failure. Eligible participants will be sent a text link to download the study smartphone app.

5.11 Changes to referral and screening process due to Covid-19 – Addition of remote screening option

Due to Covid-19 and closure of The University of Auckland campuses until the end of July, a remote referral and screening process has been devised to allow the study to continue during this period and ensure the safety of study participants and staff. This remote screening option will be offered to any participants recruited through self-referral methods such as market research surveys and Facebook who are not able to attend a clinic for screening measurements. Instead of attending a face to face clinic the participant will be screened over the phone and, if eligible,

Not for Public Circulation or Reproduction

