5.16 Physical measurements

Blood pressure, height and weight at screening

Blood pressure, height and weight will be measured at referral by either a trained GP, nurse, pharmacist, or RA. Height will be measured using a standard stadiometer to the nearest 1cm. Blood pressure will ideally be measured seated after 5 minutes rest using an automated BP monitoring device. Three BP measurements will be taken from which the average of the second two measures will be calculated. However, to minimise burden on GPs, nurses, and pharmacists, at least two measures will be enough for referral.

Not for Public Circulation or Reproduction

Urine sample collection

Baseline and follow up spot (casual) urine samples will be collected as described for the baseline phase of the study.

Home based BP measures

Baseline and follow up home-based BP measures will be collected as described for the baseline phase of the study.

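### Minor, low-cost improvement: the primary model could also adjust for gender and body weight, both recorded before randomisation; the model as stated is valid and meets its power target.

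*Protocol*

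**What the plan says.** Protocol 6.2.2 fixes the primary analysis: "The primary outcome will be analysed using linear regression model adjusting for baseline outcome value and stratification factors". The overview states the same model. The stratification factors in 5.5 are ethnicity (Māori, non-Māori) and age (under 55, 55 and over). The outcome (5.17) is estimated 24-hour urinary sodium in mg per day.

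The baseline outcome value comes from one casual spot sample, taken at any time of day other than first void (5.13).

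Two further variables are on record before randomisation:
- **Gender** (5.10): "The screening questionnaire will collect date of birth and gender", in four categories that include gender diverse and an option not to specify.
- **Weight** (5.16 Physical measurements): "Blood pressure, height and weight will be measured at referral by either a trained GP, nurse, pharmacist, or RA". Under the remote option in 5.11, weight is self-reported, either measured at home or taken from a GP record up to three months old.

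Section 6.2.2 specifies multiple imputation by MCMC under multivariate normality and missing at random. It does not list the variables in the imputation model.

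The sample size in 6.1 takes no credit for covariates: "A total of 326 participants (163 per group) will provide 80% power" "to detect a minimum effect size of 0.33 standard deviation (SD) in the primary outcome measure", using the "SD derived from the SaltSwitch pilot study data (1400mg/day") and "allowing for 10% loss to follow-up".

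**The concern.** The outcome is an amount per day, not scaled for body size, in adults of any sex and weight. The only continuous covariate in the model is a single, time-dependent spot value, which tracks a person's usual level imperfectly. Stable differences between people therefore probably remain in the residual, and gender and weight might account for some of them.

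Pre-specified adjustment for variables measured before randomisation does not bias the treatment comparison in a linear model. It narrows the interval to the extent that they predict the outcome. The data are already collected, so what is at stake is some precision on the primary estimate, and on the ethnicity and age interaction tests that 6.2.2 runs within the main model.

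**Working it through.** **Inputs from the protocol (6.1).** Two-sided 5% level, 80% power, effect 0.33 SD, SD 1400 mg/day (0.33 × 1400 = 462 mg/day), 163 per arm, 10% loss. Evaluable per arm: 163 × 0.9 = 146.7.

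**Inputs not in the protocol, so assumed.** r is the correlation between baseline and week-12 values, taken as 0, 0.3 and 0.5. q is the share of the residual variance that gender and weight explain once baseline and strata are in the model, taken as 2%, 5%, 10% and 15%.

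**Step 1: reproduce the stated size.** A two-sample t-test needs 145.1 per arm, so 146. Then 146/0.9 = 162.2, so 163 per arm and 326 in total, as stated. This is an unadjusted comparison. Power at 146.7 per arm is 80.4% from the non-central t distribution (80.7% by normal approximation).

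**Step 2: power with covariates.** The residual SD, as a fraction of 1400 mg/day, is √[(1 − r²)(1 − q)]. The standardised effect becomes 0.33/√[(1 − r²)(1 − q)]. For example, r = 0.3 and q = 0.10 give a residual SD of √(0.91 × 0.90) = 0.905 and an effect of 0.33/0.905 = 0.365. Power from the non-central t distribution:

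| r | q = 0 (stated model) | q = 2% | q = 5% | q = 10% | q = 15% |
|---|---|---|---|---|---|
| 0 | 80.4% | 81.2% | 82.4% | 84.4% | 86.3% |
| 0.3 | 84.0% | 84.7% | 85.8% | 87.5% | 89.3% |
| 0.5 | 90.2% | 90.8% | 91.6% | 92.9% | 94.2% |

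**Step 3: interval width.** The width scales with √(1 − q), whatever r is. The reductions are 1 − √0.98 = 1.0%, 1 − √0.95 = 2.5%, 1 − √0.90 = 5.1% and 1 − √0.85 = 7.8%.

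**Step 4: cost if the covariates explain nothing.** Three extra degrees of freedom out of about 290 cost less than 0.01 percentage points of power.

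**Step 5: dependence on the spot-to-24-hour conversion.** The only conversion in the protocol is the one behind the pilot SD in 6.1, a standard urine volume of 1.99 L. The protocol does not fix the conversion for this trial.
- *Fixed volume.* The outcome is a sodium concentration times a constant. Body size does not enter through volume, and q may be near zero.
- *An equation containing sex or body size.* These enter both the baseline and the week-12 value, and a noisy baseline absorbs them only in part. As an illustration, suppose they make up 20% of outcome variance and the remaining 80% has a within-person correlation of 0.3. Then r = 0.20 + 0.80 × 0.3 = 0.44. The residual variance is 1 − 0.44² = 0.806 with baseline alone and 0.80 × (1 − 0.3²) = 0.728 with both. So q = 1 − 0.728/0.806 ≈ 0.10.

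**The case against.** The strongest reply is that nothing here is wrong. Baseline plus stratification factors is a standard, pre-specified model. It is stated in the same way in both places, gives an unbiased treatment estimate, and reaches its power target before any covariate is credited. All of that stands. A reader might infer from the omission that the primary analysis is deficient or the trial underpowered, and the protocol supports neither reading.

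A reader might also take it as established that precision is lost. It is not: q appears nowhere in the protocol, and at q = 2% the gain is under one percentage point of power. Holding q constant as r rises may be generous too, because a more informative baseline could absorb more of what gender and weight predict.

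A third tempting reading is that the imputation model excludes gender and weight. Section 6.2.2 says only that the imputed datasets are analysed with the same regression models. It does not list the imputation variables, and the statistical analysis plan, which is not at hand, may do so.

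On practicality, the recorded variable is gender and not sex, sparse categories fit poorly in a multivariate normal imputation, and weight comes from mixed sources. These points call for a coding rule but do not remove the case for adjustment. Error in a baseline covariate weakens the gain in precision without biasing the randomised comparison.

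What survives is that 6.2.2 fixes the covariate set, so this is a choice made in the protocol, and the two candidate variables cost nothing further to collect. The 80% target also rests on 10% loss. If loss were 20% (an assumption; 163 × 0.8 = 130.4 per arm), power at r = 0.3 would be 79.5% under the stated model, 81.5% at q = 5% and 83.5% at q = 10%.

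**Conclusion.** This is a minor, optional improvement in precision. The gain is about 1% to 8% in interval width if gender and weight explain 2% to 15% of the residual variance. In power that is 0.8 to 5.9 percentage points at r = 0, 0.7 to 5.3 at r = 0.3 and 0.6 to 4.0 at r = 0.5. Both r and q are assumptions. If the trial converts with a fixed 1.99 L volume, the gain may be near zero; with an equation that contains sex or body size, it could lie towards the middle of the range. The loss if the covariates turn out to be uninformative is negligible. The validity of the primary analysis and the stated sample size are not in question.

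**What to change.** Before allocations are merged with outcome data:
- In 6.2.2 and the overview, extend the covariate list of the primary model to baseline outcome value, stratification factors, gender and screening body weight. Use the weight from referral or remote screening, not the self-reported weight change collected at follow-up.
- Name the same covariates in the imputation model.
- Set a simple rule in advance for sparse or unspecified gender categories and for missing weight.
- Keep the model with baseline and strata only as a supportive analysis.

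The cost is one or two sentences in the protocol or statistical analysis plan, and no new data. The downside is small: some weights are self-reported, and gender needs the coding rule.
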